8.0 SUBJECT FLOW CHART

9.0 RISK ANALYSIS

9.1 POTENTIAL RISKS

The LINX Reflux Management System has been previously studied and known risks associated with the surgical procedure and device implant can be found in the Instructions for Use (**Appendix A**). The proposed study will monitor the subjects through 12-months after implant for adverse events.

9.2 POTENTIAL BENEFITS

The potential benefits to subjects being implanted with the LINX device are the reduction or elimination of GERD-related symptoms and to reduce or eliminate dependence on GERD medications.

10.0 STATISTICAL PLAN

No formal statistical hypotheses were pre-defined for this study. Summary statistics are used to display results of effectiveness outcomes at each study time point. For categorical parameters, this includes the number and frequency; and for continuous parameters, the mean, median, standard deviation, range and 95% confidence limits are presented. For continuous efficacy parameters, the p-value for a one-sample, paired t-test to test if there is statistical evidence that the change from baseline is $\neq 0$ is also given.

10.1 EFFICACY

Efficacy will be measured by a comparison of GERD control before and after placement of the LINX Reflux Management System defined by esophageal pH measurements, GERD-HRQL score and PPI use. Subjects will serve as their own control. The change from baseline by follow-up will be calculated and summarized.

10.1.1 ESOPHAGEAL ACID EXPOSURE

Testing will be performed with subjects off PPIs. The subject's total distal esophageal acid exposure time will serve as the control and will be compared to results at the 12-month visit. Normalization for total distal ambulatory esophageal pH testing is defined as pH < 4 for < 4.5% of the time. If longer pH evaluations are received the total distal acid exposure time will be recorded as a 24 hour average (e.g. 48 hour Bravo testing). Note: The same testing equipment used at baseline should be used at subsequent follow-ups if possible.

10.1.2 QUALITY OF LIFE

Subjects GERD-HRQL (Health Related Quality of Life) scores will be assessed off all GERD medications. The subject's baseline GERD-HRQL score will serve as the control and be compared to the subject's GERD-HRQL 12 months post implantation.

10.1.3 USE OF PPIS

Subject's average daily dose of PPI will be evaluated. The subject's baseline average daily dosage will serve as the control and be compared to the subject's average daily dosage 12 months post-procedure.

10.2 SAFETY

Safety will be assessed by the rate of (number and percentage of subjects experiencing) device and/or procedure related adverse events after LINX

placement out to 12 months. Esophageal anatomy and functionality will be monitored by performing manometry and barium esophagram at 12-months post-implant. This will allow for identification of any abnormal or atypical findings. Further, device migration will be assessed by confirming device position at the GEJ by obtaining upright, bi-plane X-rays and device erosion will be assessed by performing endoscopy at the 12 month visit. Incidence of device migration and erosion will be compared to current incidence rates (i.e. zero documented incidents of device migration and a low but established occurrence of esophageal erosions) to assess concurrence of the safety profile of study subjects to that of patients without a prior LSG.

10.3 ADDITIONAL ANALYSES

- Summary statistics for components of the DeMeester score at 12 months
- Percentage of subjects who discontinue daily PPI use at 3, 6 and 12 months.
- Percentage of subjects who eliminate moderate or severe regurgitation as assessed by the Foregut Symptoms Questionnaire (FSQ) at 3, 6 and 12 months.
- Percentage of subjects with extra-esophageal symptoms as assessed by the FSQ at 3, 6 and 12 months.
- Percentage of subjects with esophagitis by endoscopy at 12 months.

Side effects will be assessed by subject questionnaires including the following:

- Percentage of subjects with ability to belch at 3, 6 and 12 months.
- Percentage of subjects with ability to vomit at 3, 6 and 12 months.

10.4 SUBJECT POPULATION FOR ANALYSIS

All subjects who meet the eligibility criteria, provide informed consent, complete baseline assessments and undergo the LINX procedure will represent the study population for analysis. Data analyses will be performed on available data at the follow-up visits.

11.0 STUDY PROCEDURES AND MANAGEMENT

11.1 CLINICAL STUDY REGISTRATION

The study will be registered by the Sponsor at www.clinicaltrials.gov.

11.2 STUDY CENTER SELECTION AND PARTICIPATION

Study centers interested in participating in this study will be assessed for their ability to fully and appropriately participate in the study. In general, study centers will be selected if patient volume is adequate to support enrollment of patients into the study and the participating physician(s) are qualified by education, training and surgical experience.

No site will enroll more than 6 subjects without prior written approval provided by the Sponsor.

11.3 INFORMED CONSENT

Prior to IRB submission, the Investigator or designee will prepare an Informed Consent Form (ICF) in accordance with this study protocol and all regulatory requirements (e.g. where applicable, 21 CFR Part 50 and in accordance with the Declaration of Helsinki) using the sample ICF provided (**Appendix C**). A copy of the final IRB approved ICF must be submitted to Torax Medical and a site must be activated by Torax Medical prior to enrolling patients at that investigational center. All study patients (or their legal guardian) must document their consent by signing an IRB-approved ICF prior to completing any protocol-specific assessments that are not considered standard of care.

11.4 INSTITUTIONAL REVIEW BOARD

This protocol, informed consent form (ICF), and authorization for the use and disclosure of health information (as applicable) must be reviewed and approved by the study center's IRB before any study patient is enrolled. Changes to the protocol must be approved in writing by Torax Medical and the IRB (as applicable) before the change is implemented.

Prior to study patient enrollment, a signed copy of the IRB approval letter addressed to the Investigator and the final approved ICF must be submitted to Torax Medical. The letter should reference this protocol by title, date or number/revision number as well as the approved ICF and HIPAA Authorization (as applicable). Investigators are responsible for submitting and obtaining initial approval and continuing approval from the IRB and forwarding copies of the approval letters to Torax Medical. The original letters are to be kept in the study center's regulatory file designated for this study.

The Investigator will notify the Sponsor within five (5) working days of withdrawal of IRB approval.

11.5 SITE ACTIVATION

A study center may not begin enrolling subjects until the Sponsor provides notification that the site has provided all required study start-up documents and completed training. At minimum, the Principal Investigator at the study center will be notified in writing of "Site Activation" when start-up activities have been completed. Upon receipt of this notification, the study center may begin enrolling subjects.

11.6 STANDARD OF CARE

As part of screening/baseline, all patients will undergo the standard of care anti-reflux surgery work-up. The anti-reflux surgery work-up used for the study enrollment should be completed within the 1-year time period prior to signing of the study ICF. For purposes of the study, the questionnaires (GERD-HRQL,

Foregut Symptom Questionnaire, and RDQ) will be considered standard of care to facilitate pre-screening of patients. However, only questionnaires completed by a subject who has provided informed consent for the study will be accessible to the Sponsor.

11.7 SCREENING/ENROLLMENT

Potential study subjects will be identified from the Investigator's practice or by referral. During the screening/enrollment visit, informed consent will be obtained prior to any study specific assessments and eligibility against the inclusion and exclusion will be confirmed prior to implant.

11.8 DEVICE TRACKING

Devices used for the study will be tracked (by lot number and number of beads) and captured on the case report forms.

11.9 ADVERSE EVENT REPORTING

If an intraoperative decision is made to not implant the LINX device, the subject will be monitored for procedure related adverse events for a period of at least three months (90 days) or longer if needed until resolution before withdrawing the subject from the study.

If a decision is made to explant the LINX device during the study, the subject will be monitored for explant-related adverse events for a period of at least three months (90 days) or longer if needed until resolution before withdrawing the subject from the study. No other study testing and/or questionnaires would be required after the device is explanted.

For all other subjects starting at the time of implantation and proceeding throughout the duration of the follow-up period, the Investigator will closely monitor each subject for the development of device and/or procedure related adverse events. A subject presenting with new onset dysphagia, abdominal pain, nausea, or vomiting, may be assessed for device migration and/or erosion if symptoms persist and benign causes cannot be established, at the discretion of the Investigator. This may include additional, non-study visit, x-rays or endoscopic evaluation. Adverse events will continue to be monitored at each of the study follow ups until resolution and/or study completion.

For the purposes of this study, a reportable event will be defined as any untoward medical occurrence which has a strong relationship to the LINX device and/or implant procedure and another etiology is unlikely. The Investigator must decide whether each event meets the definition of a Serious Adverse Event (SAE). All device and/or procedure related serious adverse events (SAE) must be reported immediately (within 5 days of discovery) to Torax Medical. SAE reporting to the IRB is per institutional policy.

An AE is considered **serious** if it meets one or more of the following criteria:

- **Is life-threatening or results in death**
Note: The term “life-threatening” in the definition of “serious” refers to an event in which the subject was at risk of death at the time of the event; it does **not** refer to an event that hypothetically might have caused death if it were more severe.
- **Requires subject hospitalization > 24 hours**
- **Requires prolongation of an existing hospitalization**
- **Results in persistent or significant disability/incapacity**
- **Results in fetal distress, fetal death, or a congenital anomaly or birth defect**
- **Requires intervention to prevent permanent impairment or damage of body function or structure**
- **Other serious important medical events that do not fit in the other outcomes and may jeopardize the patient and may require medical or surgical intervention to prevent one of the other outcomes**

Unanticipated Adverse Device Effects

Unanticipated adverse device effects (UADEs) include any serious adverse effects on the health or safety of a study subject or any life-threatening problem or death caused by, or associated with, the LINX device that are not typically associated with the procedure or the device. All unanticipated adverse device effects must be reported to the IRB within 10 working days and to Torax Medical within 24 hours after the Investigator first learns of the adverse device effect.

The following definitions for rating the severity of adverse events will be used:

Mild	Awareness of signs of symptoms, but easily tolerated; are of minor irritant type; causing no loss of time from normal activities.
Moderate	Discomfort intense enough to cause interference with usual activities.
Severe	Incapacitating with inability to do work or usual activities.

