6.2 EXCLUSION CRITERIA

Subjects should be excluded from the study based on the following criteria:

1. The procedure is an emergency procedure.
2. Suspected or known allergies to titanium, stainless steel, nickel, or ferrous materials.
3. Presence of >3 cm hiatal hernia as determined by endoscopy or barium esophagram.
4. Subject had any major complications related to the laparoscopic sleeve gastrectomy that may interfere with, or increase the risks of the LINX procedure (such as, but not limited to, leaks from the gastric remnant and infection at the sleeve gastrectomy)
5. Plans to surgically revise the gastric pouch (either known preoperatively or decided intraoperatively)
6. Currently being treated with another investigational drug or investigational device.
7. Suspected or confirmed esophageal or gastric cancer or prior gastric or esophageal surgery or endoscopic intervention for GERD (with the exception of sleeve gastrectomy).
8. Distal amplitude <35 mmHg or <70% peristaltic sequences (if using Conventional Manometry)

-or-

If using High Resolution Manometry (exclude for any of the following):

- Distal Contractile Integral (DCI) ≤ 450 mmHg·s·cm or
- $\geq 50\%$ ineffective swallows or
- $\geq 50\%$ fragmented swallows

(Fragmented swallows are defined as those with a ≥ 5 cm break [large] in peristaltic integrity)

9. Presence of esophagitis – Grade C or D (LA Classification).
10. BMI >35.
11. Symptoms of dysphagia more than once per week within the last 3 months.
12. Diagnosed with Scleroderma.
13. Diagnosed with an esophageal motility disorder such as but not limited to achalasia, nutcracker esophagus, or diffuse esophageal spasm or hypertensive LES.
14. Subject has a history of or known esophageal stricture or gross esophageal anatomic abnormalities (Schatzki's ring, obstructive lesions, etc.)
15. Subject has esophageal or gastric varices
16. History of/or known Barrett's esophagus.
*Note: The diagnosis of Barrett's esophagus requires both **endoscopic** and **histologic** evidence of metaplastic columnar epithelium. Endoscopically, there must be columnar epithelium within the esophagus. Histologically, the epithelium must be metaplastic, as defined by the presence of goblet cells.*
17. Subject cannot understand trial requirements or is unable to comply with follow-up schedule
18. Pregnant or nursing, or plans to become pregnant during the course of the study.

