Interval windows are not defined for the purpose of analysis in this study outside of the visit windows that are provided in the Study Schedule and Assessments in the final protocol. There will be no assigning of observations to time points outside of the visit to which they are recorded in the electronic Case Report Forms (eCRFs). Data collected in Unscheduled Visits forms will be listed as such. Observations collected outside of the 12-month protocol-specified visit window may be still be included in the analysis of primary effectiveness and safety endpoints since the device under study is an implant and longer term follow-up (i.e. beyond 12-months) is still considered informative towards evaluating the overall benefit-risk profile of the device in subjects with prior LSG surgery.

5 Levels of Significance

No formal statistical hypotheses are specified for this study. For continuous efficacy parameters, the p-value for a one sample, paired t-test to test if there is statistical evidence that the change from baseline is not equal to zero will be given. All estimation of endpoints will be performed using 95% confidence intervals.

6 Analysis Sets

All subjects who meet the eligibility criteria, provide informed consent, complete baseline assessments and undergo the LINX procedure will represent the study population for analysis. This set of subjects will be labeled as Full Analysis Set (FAS). This set of subjects will be identified by having answered “Yes” to the question “Was the LINX device implanted?” on the Implant Data eCRF.

7 Sample Size Justification

No formal sample size calculation has been performed for this study. The sample size planned for the study is up to 30 eligible subjects recruited from 12 clinical sites and no site will enroll more than 6 subjects without prior written approval provided by the Sponsor. No formal hypothesis has been tested in this study; thus, the sample size is not statistically sized, but rather is considered

sufficient for a descriptive summary of LINX performance for subjects who have had prior gastric surgery with LSG through confidence interval estimation and evaluation of safety and efficacy.

8 Analyses to be Conducted

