8.1 General Conventions

Subject data will be summarized in tables and presented in further detail in listings. All eCRF data will be listed per subject for all subjects. Descriptive statistical analyses will be provided for pre-specified study endpoints. Summaries for continuous variables will include a minimum of number of observations (n), mean, standard deviation, median, minimum and maximum. Summaries for categorical variables will include number and frequency.

Analyses will be conducted using SAS software. During the course of programming of tables that are mocked up in this SAP, minor modifications may become necessary. Examples of these minor modifications include, but are not limited to, table title, re-wording of a footnote, addition of a footnote, re-labeling of a column, or addition or removal of a column from a listing. In cases where modifications to tables or listings are not related to a change in statistical analysis methodology or conclusions that could be made on the originally proposed methodology, then no amendment of the SAP is necessary. Any final analyses that differ from what has been specified in this document will be identified within the final statistical output and documented within the clinical study report.

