Yes	xx (xx.x%)	xx (xx.x%)	xx (xx.x%)	xx (xx.x%)
No	xx (xx.x%)	xx (xx.x%)	xx (xx.x%)	xx (xx.x%)
No need to vomit	xx (xx.x%)	xx (xx.x%)	xx (xx.x%)	xx (xx.x%)
Ability to belch				
Yes	xx (xx.x%)	xx (xx.x%)	xx (xx.x%)	xx (xx.x%)
No	xx (xx.x%)	xx (xx.x%)	xx (xx.x%)	xx (xx.x%)

Denominator and percentages are based on subjects with non-missing data.

Table 18
 Regurgitation Severity Elimination from Severe and Moderate (Off PPI)
 Full Analysis Set

Change from Baseline	3 Months Follow-Up (N = ##)	6 Months Follow-Up (N = ##)	12 Months Follow-Up (N = ##)
Eliminate severe (to moderate, mild or none) [1]	xx (xx.x%)	xx (xx.x%)	xx (xx.x%)
Eliminate moderate (to mild or none) [2]	xx (xx.x%)	xx (xx.x%)	xx (xx.x%)

Column header counts represent the number of subjects who complete the FSQ form at the given visit.

[1] Percentages are calculated using the number of subjects with severe regurgitation at baseline and who complete the FSQ form at the given visit.

[2] Percentages are calculated using the number of subjects with moderate regurgitation at baseline and who complete the FSQ form at the given visit.

Table 19
 Regurgitation Frequency Summary (Off PPI)
 Full Analysis Set

Frequency	Baseline (N = ##)	3 Months Follow-Up (N = ##)	6 Months Follow-Up (N = ##)	12 Months Follow-Up (N = ##)
Regurgitation (times/week)				
n	xx	xx	xx	xx
Mean (SD)	xx.x (xx.x)	xx.x (xx.x)	xx.x (xx.x)	xx.x (xx.x)
Median (Min, Max)	xx.x (xx, xx)	xx.x (xx, xx)	xx.x (xx, xx)	xx.x (xx, xx)

Table 20
Adverse Events Summary
Full Analysis Set

Adverse Event Category	Number of Subjects (N = ##)	Number of Events
Any Adverse Events	xx (xx.x%)	xx
Serious Adverse Events	xx (xx.x%)	xx
AE related (Yes/Probably/Possibly or Unknown) to Study Device	xx (xx.x%)	xx
AE related (Yes/Probably/Possibly or Unknown) to Implant Procedure	xx (xx.x%)	xx
SAE related (Yes/Probably/Possibly or Unknown) to Study Device	xx (xx.x%)	xx
SAE related (Yes/Probably/Possibly or Unknown) to Implant Procedure	xx (xx.x%)	xx

All percentages are calculated using the number of subjects in the FAS as the denominator.

Table 21
All Adverse Events
Full Analysis Set

Adverse Event Category	Number of Subjects (N = ##)	Number of Events
Total	xx (xx.x%)	xx
Achalasia	xx (xx.x%)	xx
Allergic reaction	xx (xx.x%)	xx
Anaphylaxis	xx (xx.x%)	xx
....	xx (xx.x%)	xx

All percentages are calculated using the number of subjects in the FAS as the denominator.

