< Programming note: Explants are identified from the Adverse Event case report form under the "EXPLANT" checked (variable name AEEXPLANT), or in the Subject Withdrawal/Study Completion case report form under the "Reason for Withdrawal/Completion is Investigator withdrawal" selected "Device explant" (variable name DSINVESWIT=1). Time to explant in months is calculated based on either the date of explant from the AE form and the date of original implant = (AEINTERDAT1 - IMPLANTSURGDAT)/30.4375; or the date of explant mentioned in detailed reason for withdrawal/completion = (explant date derived from DSREAS1 - IMPLANTSURGDAT)/30.4375. >

Table 29
Daily PPI Use
Full Analysis Set

Characteristic	3 Months Follow-Up (N = ##)	6 Months Follow-Up (N = ##)	12 Months Follow-Up (N = ##)
Discontinue Daily PPI Use			
Yes	xx (xx.x%)	xx (xx.x%)	xx (xx.x%)
No	xx (xx.x%)	xx (xx.x%)	xx (xx.x%)

Percentages are calculated using the total number of subjects completed the 3 months, 6 months, and 12 months follow-up.

<Programming note: Discontinue Daily PPI Use is defined as subjects who reported PPI medication usage at screening/baseline but no PPI usage in each follow-up visit. (GERDMEDPPI =Yes and MEDFUPPI =No)>

The following listings will be generated for this study:

Listing 1	Inclusion/Exclusion Criteria All Subjects
Listing 2	Demographics Full Analysis Set
Listing 3	Study Visit Assessment Full Analysis Set
Listing 4	Physical Examination Full Analysis Set
Listing 5	pH Results Full Analysis Set
Listing 6	Manometry/Motility Results Full Analysis Set
Listing 7	Endoscopy Data Full Analysis Set
Listing 8	Implantation Data Full Analysis Set
Listing 9	Barium Esophagram Data Full Analysis Set
Listing 10	GERD Medications Full Analysis Set
Listing 11	LSG and GERD History Full Analysis Set
Listing 12	Motivation for Surgery Full Analysis Set
Listing 13	GERD-HRQL Questionnaire (on PPI) Full Analysis Set
Listing 14	GERD-HRQL Questionnaire (off PPI) Full Analysis Set
Listing 15	Abdominal/Chest X-Rays Data Full Analysis Set

Listing 16	Discharge Full Analysis Set
Listing 17	Follow-Up GERD Medications Full Analysis Set
Listing 18	GERD-HRQL Questionnaire Full Analysis Set
Listing 19	Foregut Symptoms Questionnaire Full Analysis Set
Listing 20	Adverse Event Full Analysis Set
Listing 21	Protocol Deviations All Subjects
Listing 22	Subject Withdrawal/Study Completion All Subjects
Listing 23	Unscheduled Visit All Subjects

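### Procedure-related adverse events after an abandoned implant are monitored under Protocol 11.9 but have no place in SAP Tables 20 and 21, or in Listing 20 as headed (minor)

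*Protocol*

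**What the plan says.** **Monitoring.** Protocol 11.9 states: "If an intraoperative decision is made to not implant the LINX device, the subject will be monitored for procedure related adverse events". The period is at least 90 days, longer if an event has not resolved, and only then is the subject withdrawn. Protocol 5.0 and SAP 1.2 start safety evaluation at the implant procedure. Protocol 6.2, exclusion 5, gives one foreseeable route to an abandoned implant: "Plans to surgically revise the gastric pouch (either known preoperatively or decided intraoperatively".

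**Analysis set.** Under Protocol 10.4, eligible and consented subjects who have finished baseline testing and who "undergo the LINX procedure will represent the study population for analysis". SAP section 6 repeats this, names the group the FAS, and then identifies it by a Yes to "Was the LINX device implanted" on the Implant Data eCRF. SAP section 6 defines no other set.

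**Tables and listings.** Tables 20 and 21 are headed FAS and carry the footnote "All percentages are calculated using the number of subjects in the FAS as the denominator". Table 20 has separate rows for AEs and for SAEs related to the implant procedure. The entry for Listing 20 reads "Adverse Event Full Analysis Set", while Listings 1 and 21 to 23 are headed All Subjects. SAP 8.1 says "All eCRF data will be listed per subject for all subjects". Table 1 counts subjects in whom no device was implanted but carries no adverse-event data.

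**The concern.** The protocol follows a group of subjects for one purpose, procedure-related harm, and the flag that builds the AE tables removes that group. The study is meant to support a label statement on safety after sleeve gastrectomy, and its safety measure covers procedure-related as well as device-related events. A complication in an operation that was begun but not completed bears on that statement. As planned, it would be absent from the rows that report procedure-related events, and a reader of Table 20 could not tell whether any such case existed.

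**Working it through.** The documents state no AE rate or calculated sample size on this point, so there is no figure to reproduce. The check is a reading of the set definitions, followed by an illustration of size.

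**Following one subject through the plan.** Take a consented subject with baseline complete, in whom surgery is begun and the implant is then abandoned.

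1. Protocol 11.9: monitored for procedure-related AEs for at least 90 days.
2. Worded population (Protocol 10.4, SAP 6): unclear, because neither document says whether an abandoned attempt counts as undergoing the procedure.
3. Operational flag (SAP 6): the answer is No, so the subject is outside the FAS.
4. Tables 20 and 21: 0 added to the numerator and 0 to the denominator, whatever events occur.
5. Listing 20: excluded by its heading, included by SAP 8.1. The two conflict.
6. Table 1: counted, but with no AE content. If the cause was exclusion 5 decided during surgery, the subject also fails the opening condition of SAP 6, "All subjects who meet the eligibility criteria". Table 1 does not say whether such a subject is a screen failure or a subject without an implant.

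**Size for one abandoned case.** Inputs: 30 implanted subjects (the planned maximum in Protocol 5.0 and SAP 7, assumed reached), one abandoned implant (assumed) and the event counts shown (assumed). Exact Clopper-Pearson 95% limits for x events in n subjects are the 0.025 quantile of Beta(x, n−x+1) and the 0.975 quantile of Beta(x+1, n−x). For x = 0 the upper limit is 1 − 0.025^(1/n); with n = 30 this is 11.6%.

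| Implanted only | Plus one abandoned case with an event | Plus one abandoned case without an event |
|---|---|---|
| 0/30 = 0% (0 to 11.6) | 1/31 = 3.2% (0.1 to 16.7) | 0/31 = 0% (0 to 11.2) |
| 1/30 = 3.3% (0.1 to 17.2) | 2/31 = 6.5% (0.8 to 21.4) | 1/31 = 3.2% (0.1 to 16.7) |

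One omitted event moves the rate by about 3 percentage points. An abandoned case without an event lowers the rate or its upper limit slightly.

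**How likely it is to matter.** Let p be the chance that an attempt is abandoned, assumed to be 1% to 5%.

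- Any abandoned implant before 30 are completed: 1 − (1 − p)^30. At 1% this is 1 − 0.99^30 = 26%; at 5%, 1 − 0.95^30 = 79%.
- An abandoned implant with an event, if a share e = 10% of such subjects has one (assumed): 1 − [(1 − p)/(1 − p + p·e)]^30. At 1% this is 1 − (0.990/0.991)^30 = 3%; at 5%, 1 − (0.950/0.955)^30 = 15%.

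**The case against.** The strongest reply is that the FAS is the population the protocol asks for. Protocol 5.1 and the synopsis word safety as post-implant, and Protocol 10.2 as after LINX placement, in each case for procedure-related as well as device-related events. Following a subject does not by itself put that subject in the reported rate. This stands: a reader might infer that Tables 20 and 21 use the wrong denominator and must be rebuilt, and the documents do not support that. What remains is that safety evaluation starts at the procedure, that 11.9 singles these subjects out for follow-up, and that the visible AE tables have nowhere to show the result.

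The second reply is that the SAP partly covers the case. SAP 8.1 promises listings for all subjects, Table 1 counts non-implanted subjects, Listings 22 and 23 cover everyone, and the shells are described as a guide whose titles may change without an amendment. This also stands. A reader might infer that such events would never be reported; that goes too far. If 8.1 prevails, they are listed but still not counted in Tables 20 and 21. The shells for Tables 22 to 28 are not in the text available to me, so I say nothing about them.

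A reader might also take the labels of Tables 20 and 21, which speak of any and all adverse events, as evidence that collection was incomplete. The synopsis refers to all adverse events, the visit schedule to device and/or procedure events without further qualification, and 11.9 defines a reportable event by a strong relationship. These scopes differ, but the eCRFs are not shown and what sites recorded is unknown. That is a labelling matter, not part of this finding.

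**Conclusion.** The gap is real and minor. As flagged, the FAS excludes every abandoned implant, so procedure-related harm in attempted but uncompleted procedures has no place in Table 20 or Table 21, and Listing 20 as headed contradicts SAP 8.1. The reading of the text is firm; the numerical effect is not. The documents do not say whether any implant was abandoned, and if none was, no result changes. One omitted event among about 30 subjects shifts the rate by about 3 percentage points. The 26% to 79% is the chance of any abandoned implant at assumed rates and should not be read as the chance of a missing event, which is about 3% to 15% under the further assumption of a 10% event share. No hypothesis test or safety threshold depends on these counts.

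**What to change.** Change the SAP only.

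- **Section 6.** Add a supplementary Procedure-Attempted Set: all consented subjects in whom the LINX procedure was started, whether or not a device was implanted and regardless of an exclusion found during surgery. State that it supplements the Protocol 10.4 population and does not replace it.
- **Table 20.** Keep the existing rows on the FAS. Add two rows, procedure-related AEs and procedure-related SAEs, on the new set with its own printed denominator.
- **Table 21.** Keep the FAS denominator, so that device-specific terms are not diluted by subjects without a device. Show event terms from abandoned implants in a separate line or note.
- **Listing 20.** Head it All Subjects, in line with SAP 8.1.
- **If no implant was abandoned,** say so, and state that the added rows equal the FAS rows.
- **Optional labelling.** Call the rows reported adverse events, and note that the synopsis, the visit schedule and 11.9 give different collection scopes that must be reconciled.

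The cost is one analysis-set flag, two rows, a note and a heading. Surgery start time is a planned field (Protocol Table 3), but the eCRF rules for abandoned cases are not visible, so a few records may need checking by hand, including screen failures attributed to exclusion 5. SAP 8.8 shows that the initial 30 subjects were already enrolled, so no protocol amendment is proposed. The procedure-related rate may look less favourable on the new set.
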